8.2.9 Epilepsy and Learning Disabilities Quality of Life Scale

The ELDQOL is a 70-item parent/caregiver/LAR-reported measure that examines seizure severity, seizure related injury, ASM side effects, behavior, mood, physical status, cognitive and social functioning, communication, overall health and quality of life, and family concerns. The higher the score, the poorer the participant's quality of life, see [Section 10.16](#).

The ELDQOL will be conducted at Visit 2 (baseline), Visit 4 (Week 1), Visit 8 (Week 5), Visit 9 (Week 9), and Visit 12 (Week 16).

Participants who continue in the OLE will also have the ELDQOL conducted at Visit 15 (Week 18) and Visit 17 (Week 20).

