Scoring the 36-Item Health Survey is a two-step process. First, precoded numeric values are recoded per the scoring key given in Table 1. Note that all items are scored so that a high score defines a more favorable health state. In addition, each item is scored on a 0 to 100 range so that the lowest and highest possible scores are 0 and 100, respectively. Scores represent the percentage of total possible score achieved. In step 2, items in the same scale are averaged together to create the 8 scale scores. Table 2 lists the items averaged together to create each scale. Items that are left blank (missing data) are not taken into account when calculating the scale scores. Hence, scale scores represent the average for all items in the scale that the respondent answered.

Table 1: Recoding Items for SF-36

Item numbers	Change original	To recoded
	response category	value of:
1, 2, 20, 22, 34, 36	1 →	100
	2 ->	75
	3 →	50
	4 →	25
	5 →	0
3, 4, 5, 6, 7, 8, 9, 10, 11, 12	1 →	0
	$2 \rightarrow$	50
	3 →	100
13, 14, 15, 16, 17, 18, 19	1 ->	0
	$2 \rightarrow$	100
21, 23, 26, 27, 30	1 →	100
	2 ->	80
	3 →	60
	4 →	40
	5 →	20
	6 →	0
24, 25, 28, 29, 31	1 →	0
	2 ->	20
	3 →	40
	4 →	60
	5 →	80
	6 →	100

Item numbers	Change original response category	To recoded value of:
32, 33, 35	1 →	0
	$2 \rightarrow$	25
	3 →	50
	4 →	75
	5 →	100

Table 2: Averaging Items to Form Scales for SF-36

Scale	Number of items	After recoding per Table 1, average the following items
Physical functioning	10	3 4 5 6 7 8 9 10 11 12
Role limitations due to physical health	4	13 14 15 16
Role limitations due to emotional problems	3	17 18 19
Energy/fatigue	4	23 27 29 31
Emotional well-being	5	24 25 26 28 30
Social functioning	2	20 32
Pain	2	21 22
General health	5	1 33 34 35 36

ELDQOL

The ELDQOL is a 70-item parent/caregiver-reported measure that examines seizure severity, seizure related injury, AED side effects, behavior, mood, physical status, cognitive and social functioning, communication, overall health and quality of life, and family concerns. The higher the score, the poorer the participant's quality of life (see Protocol Section 10.16). See the scoring instructions below:

Scoring instructions for 4 subscales of the re-validated version of ELDQOL

Seizure Severity Scale (Qs. 1 – 14)

Qs. 1, 5, 7, 8, 9, 10, 11, 13

Reverse the individual item scoring so that

- 1 = 4
- 2 = 3
- 3 = 2
- 4 = 1
- 5 define as a missing value so that it is not included in the calculation of the scale score

Qs. 4, 12

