Reverse the individual item scoring so that

- 1 = 4
- 2 = 3
- 3 = 2
- 4 = 1
- 5 = 0
- 6 define as a missing value

Qs. 2, 14

5 - Define 5 as a missing value. Other scores unchanged.

Qs. 3, 6

5 = 0

Define 6 as a missing value.

Other scores unchanged

Total scale score range = 10-56

Side-effects Profile (Qs. 17 & 18) (Only items in Q.18 used to compute sub-scale.)

Score is the sum of the individual scores for each of the 19 items in Q.18

For each item, score of 5 - define as a missing value.

Any additional problems itemised by respondents should be recorded, but are not added to the total scale score.

Total scale score range = 19-76, where high scores = high level of side effects reported.

Behaviour (Qs. 19 - 27)

Qs.19, 24, 25, 26

Define 5 as a missing value Other scores unchanged

Qs. 20, 21, 27

Reverse scoring so that:

1 = 4

2 = 3

3 = 2

4 = 1

5 - define as a missing value

Qs.22, 23

Recode so that:

5 = 4

6 – define as a missing value Other scores unchanged

Total scale score range = 9-36

Mood Scale (Q. 28)

Reverse scoring of negative items (aggressive, irritable, tearful, hyperactive, sad, agitated, restless, tantrum-prone, frustrated, withdrawn), so that:

1 = 4

2 = 3

3 = 2

4 = 1

5 - define as a missing value

Total Scale score range = 16-64

General points

For each subscale, higher score = poorer QOL / functioning.

Give non-responses a missing value (suggest 9 or -9).

The mean score for each subscale is computed as the sum of the items divided by the number of items answered. To take account of any missing data in a subscale, the mean of the completed items can be imputed, providing at least 50% of the items are completed. If more than 50% of the items in the subscale are missing, then the total subscale score should be classed as a missing value.

All scales and subscales will be summarized separately with descriptive statistics of the baseline and post-baseline values and the arithmetic changes from baseline.

Change from baseline in the percentage of seizure-free days during the DB phase, based on primary endpoint seizure type.

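### ELDQOL side-effects subscale (Q18): the SAP's unreversed sum runs opposite to its stated direction on the printed answer grid, and nothing says whether the grid or the form's conflicting instruction governs

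*SAP*

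**What the plan says.** SAP Section 4.3.5 gives the scoring key for four ELDQOL subscales. For the side-effects profile the rule is "Score is the sum of the individual scores for each of the 19 items in Q.18". The only recode is "For each item, score of 5 - define as a missing value". The stated result is "Total scale score range = 19-76, where high scores = high level of side effects reported". The general points that close the key repeat the direction for every subscale: "For each subscale, higher score = poorer QOL / functioning". Protocol Section 8.2.9 says the same of the instrument as a whole.

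The SAP refers to Protocol Section 10.16 for the questionnaire. There, the Q18 columns run Always, Often, Sometimes/rarely, Never and Can't say, over codes 1 to 5. The sentence above that grid tells the caregiver to ring 4 for a problem present always or often and 3 for one present sometimes, and leaves the lower codes unstated.

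Elsewhere the key does reverse items. In the seizure severity scale it reverses "Qs. 1, 5, 7, 8, 9, 10, 11, 13" and also Q4 and Q12. In the behaviour scale it reverses Q20, Q21 and Q27. For mood the rule is "Reverse scoring of negative items".

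**The concern.** The intended direction is not in doubt: a higher score means more side effects. The rule does not deliver that on the grid the SAP cites. Q20 and Q21 carry the same labels and codes as Q18 and are reversed; Q18 is not. The form then adds a second conflict, because its instruction runs against its own column headings.

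If the grid codes are what is stored, a worsening in caregiver-reported side effects would be tabulated as an improvement. SAP 4.3.5 plans confidence intervals for treatment differences on secondary endpoints, so the between-arm contrast would carry the same error. Three of the 19 items (unsteadiness/dizziness, tiredness, sleepiness/drowsiness) correspond to events that Protocol Section 2.2.2.2 reports more often on ganaxolone than on placebo: somnolence 23.8% vs 7.7%, dizziness 12.2% vs 3.5%, fatigue 11.2% vs 4.8%. An inverted sign would therefore matter most on the symptoms this drug is known to produce.

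**Working it through.** **Inputs.** 19 items in Q18; SAP rule: plain sum, 5 = missing (SAP 4.3.5). Grid codes: Always 1, Often 2, Sometimes/rarely 3, Never 4 (Protocol 10.16). Instruction codes: always or often 4, sometimes 3; Never is not spelled out, so I take it as 1 or 2.

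**The SAP's range.** 19 × 1 = 19 and 19 × 4 = 76, so 19-76 reproduces. Reversal maps each code c to 5 − c, which again runs from 1 to 4 and gives 19-76. The range says nothing about direction.

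**Direction.** Totals for a respondent giving the same answer to all 19 items:

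| Answer to all items | Intended (Never = 1 … Always = 4) | SAP sum, grid codes | SAP sum, instruction codes |
|---|---|---|---|
| Always | 76 | 19 | 76 |
| Often | 57 | 38 | 76 |
| Sometimes/rarely | 38 | 57 | 57 |
| Never | 19 | 76 | 19 if Never = 1; 38 if Never = 2 |

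With grid codes, intended score = 19 × 5 − SAP sum = 95 − SAP sum, so every change has its sign flipped. With instruction codes the order is right, although always and often share a code. The stated minimum of 19 fits the instruction coding only if Never = 1.

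**Illustration (assumed responses).** Baseline: 15 Never, 4 Sometimes. Later: 12 Never, 4 Sometimes, 3 Often.

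- Intended: 15 × 1 + 4 × 2 = 23, then 12 × 1 + 4 × 2 + 3 × 3 = 29; change +6.
- SAP sum, grid codes: 15 × 4 + 4 × 3 = 72, then 12 × 4 + 4 × 3 + 3 × 2 = 66; change −6.
- SAP sum, instruction codes: 27 to 36 (+9) if Never = 1; 42 to 48 (+6) if Never = 2.

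If the three items move instead to Sometimes or to Always, the intended change is +3 or +9 and the grid-code change −3 or −9. The SAP also defines a mean item score; on that scale 6 points is 6/19 ≈ 0.32, with the same sign problem.

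**Mixed answering.** If a fraction q of caregivers followed the instruction (Never = 1) and the rest the grid, the mean difference between all-Always and all-Never respondents is (1 − q)(19 − 76) + q(76 − 19). This is −57 at q = 0, 0 at q = 0.5 and +57 at q = 1.

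**The rest of the key.**

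- Reversed: 10 seizure severity items (Q1, 4, 5, 7-13), 3 behaviour items (Q20, 21, 27) and 10 negative moods, 23 in all. In every one, code 1 is the worst answer.
- Not reversed: 4 (Q2, 3, 6, 14) + 6 (Q19, 22-26) + 6 positive moods = 16. In 14 of them code 1 is the best answer. In Q3 and Q6 it is the mildest symptomatic answer; code 5, no symptom, is recoded to 0.

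The other three ranges (10-56, 9-36, 16-64) reproduce from their stated recodes. Q18 on its grid codes is the only set of items that departs from the pattern.

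**The case against.** The best defence is that a wrong sign has not been shown. It requires that grid codes are stored. That depends on the CRFs approved on 20 April 2023, on which SAP Section 2.1 relies, and these are not part of the protocol or SAP. The SAP presents its key as that of a re-validated ELDQOL version, and nothing shows whether the Appendix 16 print is that version. The form's own instruction agrees with the unreversed sum. All of this stands, and it makes the consequence conditional.

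It does not remove the textual conflict. The SAP cites the Appendix 16 form, and its rule applied to that form's grid gives the opposite of its stated direction. Nor does the instruction settle the matter: it never mentions code 5, whereas the SAP's missing-value rule matches the grid's Can't say column.

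The defence can also say that the stakes are small. The endpoint is non-key and outside multiplicity control (SAP Section 3.3), no ELDQOL test is outlined in 4.3.5, and adverse events are tabulated separately (SAP Section 6.1). That is right, and it limits the severity.

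Two stronger readings are tempting. A reader might infer that no code-to-label mapping exists. In fact the grid prints one; what is missing is a statement that it, rather than the instruction, governs. A reader might also infer that Q18 should simply be reversed. The documents do not support that, because if instruction codes are stored, reversal would create the error.

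**Conclusion.** The point holds as an internal contradiction, with high confidence. For the Q18 grid that the SAP cites, the stated scoring rule and the stated direction cannot both be right, and the form's instruction conflicts with its grid.

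The effect on results is conditional. With grid codes stored, the sign is inverted throughout the subscale. With instruction codes stored, the direction is correct. With a mixture, the score loses meaning. A reader might infer that the trial will report side effects with the wrong sign, or that a sedating drug will appear to reduce them. The documents do not establish which codes are stored, so that cannot be asserted.

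The matter should be fixed, but it is confined to one of four ELDQOL subscales in a descriptively summarised, non-key secondary endpoint. The primary, key secondary and adverse event analyses are unaffected.

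**What to change.** Before unblinding:

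1. Check the Q18 key against the scoring instructions of the re-validated ELDQOL version that the SAP names. Establish, blinded, from the CRF and database codelist which number is stored for each response label.
2. Define Q18 in the SAP by label: Never = 1, Sometimes/rarely = 2, Often = 3, Always = 4, Can't say = missing. Then all Never = 19 and all Always = 76. Apply the recode 1=4, 2=3, 3=2, 4=1 only if 1 = Always is what is stored.
3. A codelist shows what was programmed, not whether a caregiver followed the instruction or the headings. If caregivers saw the conflicting instruction and labels cannot be recovered, report the subscale with that limitation and do not interpret its direction.

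The cost is one SAP scoring line and one blinded data check. Correcting the Appendix 16 wording is optional: it changes the protocol and needs IRB/IEC approval (Protocol Section 10.1.1) across roughly 80-85 sites (Section 4.1.3), so it is best folded into any later amendment.

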LAR = legally authorized representative; Peds-QL-FIM = Pediatric Quality of Life - Family Impact Module;

PK = pharmacokinetic(s); SAE = serious adverse events; SF-36 = Short Form 36 (version 2); SQS = Sleep Quality Scale; TSC = Tuberous Sclerosis Complex.

- a Baseline is defined as the first 28 days following screening.
- b Primary endpoint seizure types are defined as the following: focal motor seizures without impairment of consciousness or awareness, focal seizures with impairment of consciousness or awareness with motor features, focal seizures evolving to bilateral, tonic-clonic convulsive seizures, and generalized motor seizures including tonic-clonic, bilateral tonic, bilateral clonic, or atonic/drop seizures. Seizures must have a motor component sufficiently prominent and distinct to clearly establish the observed symptoms as epileptic in origin. Seizures that do not count towards the primary endpoint include: focal or generalized nonmotor seizures (eg, absence seizures or focal nonmotor seizures with or without impairment of awareness), infantile or epileptic spasms, and myoclonic seizures.
- c Treatment responders are defined as those participants with a $\geq 50\%$ reduction from baseline in primary endpoint seizure frequency during the double-blind or maintenance phase.

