4. Failure to control seizures despite appropriate trial of 2 or more ASMs at therapeutic doses and for adequate duration of treatment per PI judgment.
5. Participants should be on a stable regimen of ASMs (including moderate or strong inducer or inhibitor anti-seizure medications eg, carbamazepine, phenytoin, etc.) at therapeutic doses for ≥ 28 days prior to the screening visit, and without a foreseeable change in dosing for the duration of the study. (Note: Minor dose adjustment to address tolerability and safety events may be allowed on case-by-case basis and it should be discussed with the study medical monitor.)
6. A history of at least 8 countable seizures per month in the 2 months prior to screening with no more than 1 seizure free week in each month. This includes seizures of any kind.
7. Have at least 8 primary endpoint seizures in the first 28 days following the screening visit. The primary endpoint seizure types are defined as the following:
 - a. Focal motor seizures without impairment of consciousness or awareness.
 - b. Focal seizures with impairment of consciousness or awareness with motor features.
 - c. Focal seizures evolving to bilateral, tonic-clonic seizures.
 - d. Generalized motor seizures including tonic-clonic, bilateral tonic, bilateral clonic, or atonic/drop seizures.

Seizures that **do not count** towards the primary endpoint include:

- a. Focal or generalized nonmotor seizures (eg, absence seizures or focal nonmotor seizures with or without impairment of awareness).
- b. Infantile or epileptic spasms.
- c. Myoclonic seizures.
8. Participants with surgically implanted vagal nerve stimulator (VNS) will be allowed to enter the study provided that all of the following conditions are met:
 - a. The VNS has been in place for ≥ 6 months prior to the screening visit.
 - b. The settings must have remained constant for 3 months prior to the screening visit and are expected to remain constant throughout the study.
 - c. The battery is expected to last for the duration of the study.
9. Parent(s)/caregiver(s)/LAR(s) or the participant, as appropriate, is (are) willing and able to maintain an accurate and complete daily seizure eDiary for the duration of the study.
10. Willing and able to take IP (suspension) as directed with food (tid).

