1. INTRODUCTION

This is a Phase 3, global, double-blind, randomized, placebo-controlled study of adjunctive Ganaxolone (GNX) treatment in children and adults with TSC-related epilepsy. The study consists of a 4-week prospective baseline phase, defined as the first 28 days following screening, followed by a double-blind phase consisting of a 4-week titration period and a 12-week maintenance period.

Following completion of the treatment period, participants who are compliant with study conduct will have the option to enroll and be treated with GNX in a separate OLE study, 1042-TSC-3002. All participants entering the OLE will have their dose of study medication adjusted in a double-blind cross-titration over 4 weeks such that all are receiving GNX at study completion. Participants who do not continue in the OLE will undergo a 2- to 4-week double-blind down-titration and taper if discontinuing IP.

Sections 2 and 5 of the Protocol provides a detailed description of the investigational product, target patient population, and potential risks and benefits of treatment with GNX. The purpose of this Statistical Analysis Plan (SAP) is to define the methodology for analyzing and summarizing the data collected during the conduct of Study 1042-TSC-3001.

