The percentages of seizure-free days will be based on the primary seizure types. Post-baseline percentage of seizure-free days will be calculated as the number of days in the DB treatment phase with zero seizures divided by the number of days with seizure data in the phase, multiplied by 100. The baseline percentage of seizure-free days will be calculated as the number of days in the 4-week baseline phase with zero seizures divided by the number of days with seizure data in the baseline phase, multiplied by 100.

The baseline and post-baseline values and the arithmetic changes from baseline will be summarized using descriptive statistics.

CGI-CSID at the last scheduled visit in the DB phase.

The CGI-CSID is from the 7-point Caregiver Global Impression of Change in Seizure Intensity/Duration instrument. The scores range from 1=very much improved and 7=very much worse. The number and percentage of subjects with each score will be summarized.

Participants with a $\geq 25\%$ and $\geq 75\%$ reduction from baseline in primary endpoint seizure frequency during the DB phase.

Number (%) of subjects considered treatment responders, defined as those with a \geq 25% and \geq 75% reduction from baseline in primary seizure frequency during the DB phase will be summarized.

Participants with a $\geq 25\%$, $\geq 50\%$, and $\geq 75\%$ reduction from baseline in primary endpoint seizure frequency during the maintenance period.

Number (%) of subjects considered treatment responders, defined as those with a \geq 25%, \geq 50%, and \geq 75% reduction from baseline in primary seizure frequency during the maintenance period will be summarized.

Responder analysis for primary endpoint seizures and all seizures during the double-blind phase using the following response categories: $\leq 0\%$, > 0% to < 25%, $\geq 25\%$ to < 50%, $\geq 50\%$ to < 75%, and $\geq 75\%$ to 100%.

Number (%) of subjects considered treatment responders categories, defined as those with a \leq 0%, \geq 0% to < 25%, \geq 25% to < 50%, \geq 50% to < 75%, and \geq 75% to 100% reduction from baseline in seizure frequency during the DB phase will be summarized using descriptive statistics (in both a table and a figure). The analysis will be conducted for primary endpoint seuzures and all seizures, respectively.

Percent change in 28-day frequency of all seizures.

This analysis is similar to primary efficacy endpoint during the DB phase, except all seizure types will be applied.

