Change from baseline in the percentage of seizure-free days, based on all seizure types.

The percentages of seizure-free days will be based on all seizure types. Post-baseline percentage of seizure-free days will be calculated as the number of days in the DB treatment phase with zero seizures divided by the number of days with seizure data in the phase, multiplied by 100. The baseline percentage of seizure-free days will be calculated as the number of days in the 4-week baseline phase with zero seizures divided by the number of days with seizure data in the baseline phase, multiplied by 100.

[figure not shown]
The baseline and post-baseline values and the arithmetic changes from baseline will be summarized using descriptive statistics.

[figure not shown]
Change from baseline in the longest seizure-free interval, based on primary endpoint seizure type and all seizure types.

The longest seizure-free intervals (percentage of days) will be based on both the primary seizure types and all seizure types. The post-baseline longest period of time seizure-free is defined as the longest seizure-free period (days) in the DB treatment phase divided by the days with seizure data during the phase, and then multiplied by 100%. The baseline longest period of time seizure-free is defined as the longest individual seizure-free period (days) in the baseline phase divided by the days with seizure data during the baseline phase, and then multiplied by 100%. For both phases, the longest period is based on the number of days without an interruption of a day with a seizure. If there is an interruption of a day without any seizure data, then that day will not count. For example, if there are seizures on January 1st, no seizures on January 2nd through 4th, no seizure data on January 5th, no seizures on January 6th, and there are seizures on January 7th, then the longest period of time seizure free in this interval would be 4 days (January 2nd through 4th and January 6th).

The longest seizure-free interval will be summarized using descriptive statistics for the baseline and post-baseline values, as well as the arithmetic changes from baseline.

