5.2. Definition of Baseline

The Baseline Visit is defined as Visit 2 (Day 1). Baseline values for non-seizure efficacy and safety assessments will be the last values collected prior to the first administration of IP (i.e., GNX), unless otherwise specified.

Baseline seizure frequency data is collected during the four weeks between the Screening Visit (Visit 1, Week -4) and the Baseline Visit (Visit 2, Day 1). This interval may range from no less than 28 days to no more than 34 days.

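### The longest seizure-free interval is scored as a percentage of each phase's own diary days (about 28 at baseline, 112 double-blind), so its change from baseline reads on average as worsening when nothing has changed.

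*SAP*

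**What the plan says.** SAP 4.3.5 expresses this endpoint as a percentage of days, for primary endpoint seizures and for all seizures. The double-blind value is "the longest seizure-free period (days) in the DB treatment phase divided by the days with seizure data during the phase", times 100. The baseline value is "the longest individual seizure-free period (days) in the baseline phase divided by the days with seizure data during the baseline phase", times 100. The reporting rule is: "The longest seizure-free interval will be summarized using descriptive statistics for the baseline and post-baseline values, as well as the arithmetic changes from baseline".

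The two windows differ in length. The double-blind phase is 4 weeks of titration plus 12 of maintenance, or 112 days. SAP 7 restricts the EMA analysis to maintenance, or 84 days. Baseline is 28 days in Protocol 3 ("Baseline is defined as the first 28 days following screening") and in SAP 1 ("4-week prospective baseline phase, defined as the first 28 days following screening"). SAP 5.2, however, describes the span between the screening and baseline visits thus: "This interval may range from no less than 28 days to no more than 34 days". SAP 5.3 counts back from the first dose, from Day -28 through Day 1. It also adds taper and safety visits to the 16-week treatment period for those not entering the extension.

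The protocol names the endpoint only as a change from baseline in the longest seizure-free interval. The percentage scaling enters in the SAP, and nothing there adjusts for the unequal windows.

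**The concern.** Dividing by diary days is sound for the companion endpoint, the percentage of seizure-free days ("number of days in the DB treatment phase with zero seizures divided by the number of days with seizure data in the phase"). That is a proportion, and its expected value does not depend on how long one observes. A longest run is a maximum. It lengthens slowly as the window grows, far less than in proportion, so dividing it by a window four times as long shrinks it.

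A participant whose seizures do not change is therefore expected to score a fall, and a fall on this scale means worse seizure control. The tables would tend to show both arms deteriorating, possibly while seizures were decreasing. What is at stake is the reading of one named secondary endpoint; the primary analysis does not use this score.

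**Working it through.** The documents give no figure for this endpoint to reproduce, and no typical seizure rate. Rates below are assumptions shown as a range.

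**Simplest case.** The same 4-day longest run in both phases scores 4/28 = 14.3% and 4/112 = 3.6%, a change of -10.7 points.

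**Exact expectation, no true change.** Let p be the probability that a day has a seizure, with independent days, and L(n) the longest seizure-free run in n days. P(L(n) ≤ m) comes from a Markov chain on the current run length 0 to m. Each day the run resets to 0 with probability p or grows by one with probability 1-p, and paths that exceed m are dropped. Then E[L(n)] = sum over m = 0 to n-1 of [1 - P(L(n) ≤ m)]. The score is 100 × E[L(n)]/n. The equivalent rate per 28 days is -28 × ln(1-p). Changes use unrounded values.

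| p | seizures per 28 days | baseline run, days (score) | double-blind run, days (score) | change, 112 days | change, 84 days (EMA) |
|---|---|---|---|---|---|
| 0.25 | 8 | 8.4 (30.0%) | 13.1 (11.7%) | -18.3 | -15.5 |
| 0.50 | 19 | 4.2 (15.0%) | 6.2 (5.5%) | -9.5 | -8.1 |
| 0.75 | 39 | 2.1 (7.6%) | 3.1 (2.8%) | -4.8 | -4.2 |
| 0.90 | 64 | 1.2 (4.3%) | 1.7 (1.6%) | -2.7 | -2.3 |

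**Entry rule.** Criterion 7 in Protocol 5.1 requires this: "Have at least 8 primary endpoint seizures in the first 28 days following the screening visit". Selecting on a high baseline count shortens the baseline run and offsets part of the artefact. Poisson diaries (200,000 of 140 days per rate) were kept only if the first 28 days held at least 8 seizures. The no-change score is then -12.2, -13.2, -12.7, -9.2 and -6.8 points at true means of 7, 9, 12, 20 and 28 seizures per 28 days. About 92 to 97% of these unchanged participants score a fall.

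**Real improvement.** Without the entry rule, the mean change stays negative until seizure days fall by 69%, 62%, 49% and 34% at the four values of p (EMA: 60%, 52%, 39%, 25%). A true 25% fall in seizure days reads -14.8, -7.2, -3.0 and -0.8 points. In Poisson simulation a true 50% fall in seizure rate reads -7.5, -4.7 and -3.3 points at 12, 20 and 28 seizures per 28 days. A 50% reduction is the plan's own responder threshold.

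**Between arms.** With equal diaries, a 25% fall in seizure days on GNX and none on placebo gives a difference of -14.8 - (-18.3) = +3.5 points at p = 0.25, and +2.3, +1.9 and +1.9 at the other values. The direction is right.

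**Diary length.** In simulation, an unchanged participant at 8 seizures per 28 days scores +13.7 if the diary stops at day 14, 0 if it stops at day 28, and -18.4 at day 112. At 20 seizures the figures are +8.0, 0 and -9.3.

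**Clustered days.** With lag-1 correlation of 0.2 and 0.4 and no true change, the score moves -20.6 and -23.3 at p = 0.25, -11.3 and -13.5 at p = 0.50, and -6.0 and -7.3 at p = 0.75. Independence is not what produces the artefact.

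**The case against.** The strongest reply is that a placebo-controlled trial is read between arms. SAP 4.3.5 opens by promising confidence intervals for treatment differences on the secondary endpoints, and the placebo column would show the same shift beside the GNX column. With equal diaries this is right, and it is why the point is minor. It does not repair the change score that the same section commits to report.

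Second, the largest figures belong to few likely participants. Criterion 6 allows at most one seizure-free week in each of the 2 months before screening. Read as no gap above 7 days in 56, about 19% of participants at p = 0.25 would pass, against 91% at p = 0.50. This is approximate, since criterion 6 counts seizures of any kind. The entry-rule figures, at most about 13 points, are the fairer guide near the floor. They remain clearly negative.

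Third, the effect holds on average, for long diaries. A participant with no seizure-free day at baseline cannot fall, and a short diary moves the other way. That stands. Protocol 7.2 asks those who stop treatment during maintenance to keep recording, Protocol 8.1.2 covers the taper, and SAP 4.3.3 asks for records to the end of the 16 weeks. These limit unequal diary length without ruling it out. No between-arm bias of any size is claimed.

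Fourth, a 28-day-window score is not free of drift either. Near the entry floor, regression to the mean makes no change read as a gain. That is true, and its size is given with the fix.

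**Conclusion.** The concern holds, as a minor point. As written, the change from baseline in the longest seizure-free interval cannot be interpreted within an arm: no change reads as worsening, and so does moderate improvement. The no-change shift is -18.3 to -2.7 points over the range of p shown (EMA -15.5 to -2.3), and -12.2 to -6.8 points at true means of 7 to 28 with the 8-seizure rule applied. These sizes rest on assumed seizure rates, full-length diaries and simple day-to-day models. The negative sign persisted at every rate tried with full diaries, and under clustering.

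With equal diaries the direction of the treatment difference is preserved. The endpoint is a descriptive, non-key secondary outside the testing sequence in SAP 3.3, and the primary endpoint is unaffected. The baseline window is also stated inconsistently, which matters here because its length is the denominator.

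**What to change.** - Drop the percentage scaling for the change score. Take the longest seizure-free run in days within Days 1-28, 29-56, 57-84 and 85-112 (the last three for the EMA), average over evaluable windows, and subtract the value from the first 28 baseline days.
- Report the longest run in days over the whole phase as a between-arm comparison only, so that long seizure-free spells are not lost. It should not be used as a change from baseline: against a 28-day baseline, raw whole-phase days rise with no true change, by +4.8, +1.9, +1.3 and +0.7 days at 8, 20, 28 and 56 seizures per 28 days.
- Keep the SAP rule for sporadic missing days, and state the minimum diary days for an evaluable window. The documents give none; 24 of 28 is an example.
- Show diary length, and the number with no evaluable window, by arm.
- Align SAP 4.3.5, 5.2 and 5.3 with Protocol 3 and SAP 1 on the first 28 days, and state that taper days are outside the windows.

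Expected behaviour at p = 0.25, 0.50, 0.75 and 0.90, in days and without the entry rule:

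| true fall in seizure days | window change score | whole-phase difference between arms |
|---|---|---|
| none | 0.0 at all four | 0 |
| 25% | +2.0, +1.6, +1.4, +1.5 | +3.9, +2.5, +2.1, +2.1 |
| 40% | +3.7, +3.0, +2.6, +2.6 | +7.3, +4.8, +3.9, +3.8 |

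Under the clustered-day models the no-change window score stays within 0.04 day of zero.

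The cost is SAP wording and programming; the diary data already exist. Runs are cut at window boundaries and capped at 28 days, and very short diaries have no change score. Regression to the mean from the entry rule remains: +2.2, +1.1, +0.3 and 0.0 days at true means of 7, 9, 12 and 20 seizures per 28 days. Near the floor the placebo arm is still needed to read the change. Four missing days in a window lower the run by 0.5 day at p = 0.25 and 0.2 day at p = 0.50.
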